6.3.2 Expedited Adverse Event Reporting Criteria to the IND Manufacturer

Investigators will submit reports of all SAEs, regardless of attribution to RPS within 24 hours of learning of the events. For initial SAE reports, Investigators should record all case details that can be gathered within 24 hours on a SAE Report Form and submit the report via fax to:

Research Pharmaceutical Services (RPS) Drug Safety

[contact] or (+ 1) [contact]

Relevant follow-up information should be submitted to RPS's Drug Safety Department as soon as it becomes available and/or upon request.

6.4 DATA AND SAFETY MONITORING PLAN

6.4.1 Principal Investigator/Research Team

The clinical research team will meet on a regular basis when patients are being actively enrolled on the trial to discuss each patient.

All data will be collected in a timely manner and reviewed by the principal investigator or a lead associate investigator. Adverse events will be reported as required above. Any safety concerns, new information that might affect either the ethical and or scientific conduct of the trial, or protocol deviations will be immediately reported to the IRB using iRIS and to the Sponsor.

The principal investigator will review adverse event and response data on each patient to ensure safety and data accuracy. The principal investigator will personally conduct or supervise the investigation and provide appropriate delegation of responsibilities to other members of the research staff.

6.4.2 Sponsor Monitoring Plan

Due to the “Low Risk” categorization of observational studies that use PET IND Radiopharmaceuticals, an annual monitoring of the clinical investigation will be conducted by completing the worksheet found in section **11.3**, Appendix C. The monitoring worksheet may be completed at the time of Continuing Review by the Principal Investigator or a designee (designee must be familiar with the study. Completed worksheet must be signed by the PI.

7 STATISTICAL CONSIDERATIONS

The primary objective of this prospective study is to assess the diagnostic accuracy of the new imaging technique ⁶⁸Gallium-DOTATATE PET/CT scan for patients with NETs. Based on the existing literature, the rate of correct classification of this new imaging technique against the gold standard of Octreoscan SPECT is about 85% [46, 60]. Assuming that on average 2 lesions will be evaluated for each patient, and that classifications of the multiple lesions from the same patient are modestly correlated with a correlation coefficient set at 0.2, the sample size is determined to achieve a desired precision of the estimate of the proportion of correct classification measured by the width of the 95% confidence interval. A few scenarios of sample size and true rate of correct classification are considered and listed in the following table.

Number of patients	True proportion of correct classification	95% confidence interval
50	0.85	(0.77,0.93)
100	0.85	(0.80,0.90)
150	0.85	(0.81, 0.89)
200	0.85	(0.81,0.89)
50	0.87	(0.80,0.94)
100	0.87	(0.82,0.92)
150	0.87	(0.83,0.91)
200	0.87	(0.83,0.91)

If the true proportion of correct classification is 0.85, with 50 patients, the 95% expected confidence interval is (0.77, 0.93), and with 100 patients, the 95% expected confidence interval is smaller (0.80, 0.90). The confidence interval is shortened only slightly even if the sample size is doubled to 200. This is also the case when the true proportion of correct classification is 0.87. Even though there does not appear to be a big difference in the confidence interval for the estimated accuracy of ⁶⁸Ga-DOTATATE for the sample size of 50 patients as compared to 100 patients, based on the literature [61], less than 20% of the patients are expected to have negative NETs. As a result, with the total sample size of 50 patients, likely less than 10 patients would have negative NETs, which is too small to estimate the specificity with precision. Hence the study is targeted at a sample size of 100 patients resulting in a 10% width of the 95% expected confidence interval for the estimate of the correct classification rate of ⁶⁸Ga-DOTATATE. As such, the study has an adequate size to estimate both the correct classification rate and sensitivity and specificity.

Studies have shown specificities for ⁶⁸Ga-DOTATATE PET/CT as high as 90% for primary and metastatic NETs [42, 60]. Patients included in the protocol will have yearly follow-up with

conventional imaging studies for assessment of changes in lesions which would minimize false positives. Furthermore, in patients who require surgery, diagnosis will be confirmed by histopathology.

Based on current protocols for MEN1 and VHL and patients seen by provider on these protocols, we estimate an accrual rate of 3-10 patients per month. This includes patients with VHL and pancreatic NETs and patients with MEN1. Currently the VHL protocol includes up to 220 patients followed every year, with an accrual rate of 4 new patients on average per month [range 2-7/month in 2012]. For patients with MEN1 patients, up to 200 patients are followed on a current protocol. If we assume that 50% of those patients are willing to participate and adding the new patients recruited from outside the NIH and sporadic cases, we should reach an accrual rate between 3-10 patients per month. Hence, the total length of accrual period for this study is estimated to be 10 months to 3 years.

One of the secondary objectives of the study is to determine whether DOTATATE uptake value predicts tumor and disease progression. To study this, the SUV uptake of ⁶⁸Ga-DOTATATE on PET imaging will be compared between patients who require operative intervention and those who do not, and SUV uptake will be correlated to tumor size and growth rate of the tumors. Among patients with sporadic or familial gastrointestinal and pancreatic NET to be accrued into this study, it is expected that 10-30% of them will require operative intervention. With a targeted total of 100 patients: approximately 20 requiring operative intervention and 80 not requiring operative intervention. The study would have 84% power to detect a standardized mean difference (mean difference/SD) of 0.75 in SUV uptake of ⁶⁸Ga-DOTATATE between the two groups of patients, using the two-sample t-test at the 5% significance level. Two recent published studies [46, 62] show that the variability of SUV uptake of ⁶⁸Ga-DOTATATE is large, and the standard deviation is comparable to the mean value. If the variability of SUV uptake of ⁶⁸Ga-DOTATATE of the current study is comparable to that in those previous 2 studies, then detecting a standardized mean difference of 0.7 would be close to detecting a 1.75 mean fold change.

Additionally, radio-guided surgery using a gamma probe will be used for patients that require an operation and have lesions confirmed to have positive uptake on ⁶⁸Ga-DOTATATE PET/CT. The main goal is to assess feasibility of this new technique with radio-guided surgery as this approach may facilitate the intra-operative detection of some NETs or detect additional lesions. For measurements of the uptake by the probe, the count rate signal will be used as well as the ratio between the target and the background (normal tissue). Further, the sensitivity of radio-guided surgery will be compared to pre-operative ⁶⁸Ga-DOTATATE PET/CT SUV uptake and to surgical palpation for intra-operative detection of NETs. The number of lesions and their SUVs detected on PET/CT, the number detected by the gamma probe and by visualization and surgical palpation will be compared. The final histological diagnosis will be used as the gold standard for correct identification of NETs.

Another important secondary objective of the study is to determine the relationship between somatostatin receptor status (SSRT) in tumor samples and ⁶⁸Gallium-DOTATATE uptake. Based on the existing literature [49, 63], SSTR score is approximately uniformly distributed. With 20 expected patients requiring operative intervention, the study will have 82% power to detect a standardized mean difference of 1.2 between half of the patients with low SSRT-2 scores (0-1) versus the remaining patients with high SSTR-2 scores (2-3) using the two-sample t-test at the 10% significance level. The power would be less than 80% if the standard mean difference is

less than one. The relationship between subtypes of SSRT and ⁶⁸Gallium-DOTATATE uptake will also be examined, but it is expected that they have lower affinity to ⁶⁸Gallium-DOTATATE uptake than SSRT-2. As a secondary objective, the outcome will be useful in generating hypothesis and planning for future studies.

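### Section 7 calls 100 patients an adequate size for specificity without calculating it; on the plan's own figures the 95% interval would be about 20 to 30 points wide (about 10 to 15 at the current ceiling of 390)

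*Combined protocol and SAP*

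**What the plan says.** Section 7 sizes the study on the precision of the correct classification rate. Its inputs are two lesions per patient ("Assuming that on average 2 lesions will be evaluated for each patient"), results within a patient that are "modestly correlated with a correlation coefficient set at 0.2", and a true rate of 0.85 or 0.87. A table gives the expected 95% interval for 50, 100, 150 and 200 patients.

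The section concedes that the accuracy interval differs little between 50 and 100 patients. It prefers 100 because of specificity: "less than 20% of the patients are expected to have negative NETs", so at 50 patients "likely less than 10 patients would have negative NETs, which is too small to estimate the specificity with precision". It goes on: "Hence the study is targeted at a sample size of 100 patients resulting in a 10% width of the 95% expected confidence interval", and that width is stated for the correct classification rate. It then concludes that "the study has an adequate size to estimate both the correct classification rate and sensitivity and specificity". A later sentence cites specificities for "PET/CT as high as 90% for primary and metastatic NETs".

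Sections 7.1 (Amendment D) and 7.2 (Amendment H) raise the accrual ceiling to 295 and then 390. The reasons given are the comparison of PET/CT with CT, surgical confirmation, unknown primaries and the gamma probe. Neither section mentions specificity, and the adequacy sentence remains in the current text.

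**The concern.** Specificity is the reason given for choosing 100 patients over 50, yet no specificity interval is shown for either size. The share of negatives that made 50 too small gives fewer than 20 negatives at 100. The adequacy conclusion follows directly on a width calculated for all patients and all lesions, and carries it over to a subgroup of at most one fifth of them.

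Diagnostic accuracy is the primary objective, and specificity is part of it. A reader who relies on this sentence would take a reported specificity to be about as precise as the overall rate. On the plan's own figures it would not be.

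**Working it through.** **Inputs, all from Section 7 unless noted**
- Patients: 50 (rejected), 100 (chosen); current ceiling 390 (Section 7.2).
- NET-negative share: under 20%, so at most 10, 20 and 78 negatives. The upper bound is used throughout.
- Specificity: 0.90, cited as the high end of published values.
- k = 2 lesions per patient, r = 0.2.

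**Step 1: reproduce the plan's table.** The Wald interval with a design effect is

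p ± 1.96 × √{ p(1−p)/(nk) × [1 + (k−1)r] }

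For n = 100, p = 0.85: √(0.1275/200 × 1.2) = 0.0277. The half-width is 0.0542 and the interval 0.796 to 0.904, 10.8 points wide. The plan prints (0.80, 0.90). All eight rows reproduce to two decimals. With one unit per patient the same row would be 0.78 to 0.92, which does not match, so the plan's 10 points is a lesion-based figure.

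**Step 2: specificity with 20 negatives (100 patients), at 0.90**
- Plan's formula, if each negative patient also supplies two units: √(0.09/40 × 1.2) = 0.0520; width 2 × 1.96 × 0.0520 = 20.4 points.
- Per-patient Wald: √(0.09/20) = 0.0671; width 26.3 points.
- Exact (Clopper-Pearson), 18/20: 68.3% to 98.8%; width 30.5 points.

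Both Wald upper limits pass 100% (1.002 and 1.032). That is a reason to name a method suited to small counts.

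**Step 3: all three sizes, specificity 0.90, full width in points**

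| Patients | Negatives (at most) | Plan's formula | Per-patient Wald | Exact |
|---|---|---|---|---|
| 50 | 10 | 28.8 | 37.2 | 44.2 (9/10) |
| 100 | 20 | 20.4 | 26.3 | 30.5 (18/20) |
| 390 | 78 | 10.3 | 13.3 | 14.7 (70/78: 81% to 95%) |

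Going from 50 to 100 patients narrows the interval by about 30% (1 − 1/√2 = 29% for the Wald forms; 44.2 to 30.5 exact). Even the most favourable width at 100, 20.4 points, exceeds the 16 points that the plan prints for the overall rate at 50 patients: "If the true proportion of correct classification is 0.85, with 50 patients, the 95% expected confidence interval is (0.77, 0.93").

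**Step 4: sensitivity to the inputs.** With 19 negatives instead of 20, the widths are 20.9, 27.0 and 31.8 (17/19). With 20 negatives and specificity 0.85 they are 24.2, 31.3 and 34.7 (17/20). The figures in Step 3 are therefore near best cases.

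**The case against.** The strongest reply has three parts.

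First, the 30-point figure is not the only one the plan's figures allow. The formula that reproduces its table gives 20.4 points, and setting an exact per-patient interval against a lesion-based 10-point width mixes yardsticks. On the exact per-patient basis the accepted classification rate would itself miss 10 points: 85/100 gives 76.5% to 91.4%, 14.9 points. This stands, and it is why a range by unit and method is reported. It does not rescue the claim: on the plan's own formula, like with like, specificity is 20.4 points against 10.8. That result also needs negative patients to supply two units each, which the plan does not say; it counts negatives as patients.

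Second, the plan sets no numerical criterion for adequate specificity. It says that fewer than 10 negatives is too few, and never says that fewer than 20 is. This also stands. A reader might infer that Section 7 contains an arithmetic error or fails a quantified property. It does not: no printed figure is wrong, and the defect is an adequacy claim with no calculation behind it. A reader might likewise infer that about 690 patients are needed, from 139 negatives for a 10-point per-patient Wald width at 0.90, divided by 0.20. The documents do not support this, because the 10-point width is never set as a target for specificity.

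Third, 100 is no longer the ceiling. At 390 the plan's formula gives 10.3 points, slightly narrower than the 10.8 it accepted for the classification rate. This stands as a limit on consequence. A reader might infer that the current study cannot separate a specificity of about 70% from one of 99%; that describes 100 patients only. It does not repair the text, since neither amendment restates specificity and the sentence is still there.

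**Conclusion.** The adequacy claim for specificity is not supported at 100 patients. With at most 20 negatives and 90% specificity the 95% interval is about 20 to 30 points wide, depending on unit and method: two to three times the width the plan cites, which belongs to the correct classification rate. At 390 patients, with at most 78 negatives, it is about 10 to 15 points, so the present effect is modest.

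The result rests on the plan's own bounds of 20% negative and 90% specificity. Both are upper limits, so lower values of either widen the intervals. The lowest figure in each range also assumes two units per negative patient with correlation 0.2.

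Two further inferences are not supported. It does not follow that the size is adequate for sensitivity: the plan calculates nothing there either, and with an illustrative 80 positives the exact interval for 72/80 is 81% to 96%, 14 points. Nor does it follow that specificity must be relabelled as descriptive; the documents treat it as part of the accuracy objective.

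**What to change.** In Section 7, replace the adequacy sentence with the expected number of NET-negative patients and the expected 95% interval for specificity, at 100 and at the current ceiling of 390. Name the unit (patient or lesion) and the interval method. With patient as unit, the exact method and 90% specificity, the entries would be at most 20 negatives, 68% to 99%, and at most 78 negatives, 81% to 95%. If lesions are the unit, state how many units a negative patient contributes and the correlation assumed. Add that 20% and 90% are upper bounds.

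Limit the 10-point precision statement to the correct classification rate. Make no adequacy statement for sensitivity unless an interval is calculated for it.

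The cost is a change of wording. No patients, procedures or analyses are added. The downside is that one stated property of the design becomes less favourable.

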Computed tomography (CT) has been the most widely used modality with the best sensitivities when both arterial and portal venous phases are performed for detecting pancreatic and intestinal NETs. Magnetic resonance imaging (MRI) is less accurate, identifying >50% of pancreatic NETs larger than 3cm in diameter but only 5% if the tumor was smaller than 1cm [27, 28].

Recent studies suggest functional imaging with positron emission tomography (PET) is helpful as a localizing modality. For example, ¹⁸FDG PET scans have been reported to be helpful for localizing and for possibly distinguishing malignant from benign NETs [29, 30]. However, ¹⁸FDG PET scans have limited use in well-differentiated NETs due to the low expression of glucose transporters and low proliferative activity in these tumors [31-33]. In fact, in our prospective study of patients with VHL and solid pancreatic lesions on axial imaging, ¹⁸FDG-PET only identified approximately half (46%) of the pancreatic NETs diagnosed on CT and MRI [34].

Newer functional imaging studies have emerged targeting the somatostatin receptor which is expressed in over 70% of NET cells. The current gold standard functional imaging technique for NETs is octreotide scintigraphy, targeting the somatostatin receptor 2, but with variable

Abbreviated Title: $^{68}\text{Gallium}$ Detecting Tumors

Version Date: 09/20/17

diagnostic sensitivity according to tumor site of origin, 65-100% [35, 36]. Up to five different somatostatin receptor subtypes have now been identified and studies show that gastrointestinal NETs have high expression of somatostatin receptor 2 [11, 37].

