Localization of primary tumors and detection of metastases are crucial for optimizing treatment strategies. Slow-growing PNETs are best treated by complete surgical removal, but in the presence of metastases or non-resectable disease, unnecessary surgery could be spared. Furthermore, PET with ^{68}Ga -labeled somatostatin ligands has been used as a tool in localizing unknown primary tumor in metastatic NET [43]. According to *Hofman et al.* [44], ^{68}Ga -PET was superior than octreoscan and conventional imaging (CT, MRI, bone scintigraphy) in identification of additional sites of disease, with bone and local lymph nodes being the most frequent sites. Furthermore, PET with ^{68}Ga -labeled somatostatin has been suggested to be superior to FDG PET and FDOPA PET in the detection of additional tumors [38, 45, 46]. *Frilling et al.* [47] showed SSRT- ^{68}Ga -PET/CT to be superior to CT and/or MRI, as it detected additional hepatic and/or extrahepatic metastases in 22 of 33 patients. It has been recommended as a diagnostic modality by the European Neuroendocrine Tumor Society 2012 [48], and provides staging by assessing metastases that can lead to changes in both medical and surgical management strategies [44, 47]. Although, ^{68}Ga -labeled somatostatin scintigraphy is emerging as an accurate diagnostic imaging approach, most studies in Europe are in relatively small study cohorts or retrospective. Therefore, we propose to study the accuracy of ^{68}Ga -DOTATATE imaging in patients with NET with the primary goal of determining if this modality can be used to detect unknown primary NET and can detect malignant/metastatic disease in patients with NETs. We will correlate radiologic findings of $^{68}\text{Gallium}$ -DOTATATE PET/CT to results obtained by anatomic imaging (CT/MRI) and pathologic confirmation in those patients undergoing surgical treatment. This will determine whether additional lesions can be found on $^{68}\text{Gallium}$ -DOTATATE PET/CT.

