3.1.1.2 Non-invasive imaging

- CT scan with contrast of the chest, abdomen and pelvis. Tridimensional tumor measurements will be performed on contrast CT scans to evaluate size and rate of tumor growth, on scans obtained at baseline and at each follow up visit.
- Patients with a severe iv contrast allergy (anaphylaxis with premedication) will have a MRI of the abdomen and pelvis performed and non-contrast CT of Chest instead of the CT scan (MRI of chest will only be performed if suspicious lesions seen on previous imaging or on ⁶⁸Gallium-DOTATATE PET/CT).
- ⁶⁸Gallium DOTATATE PET/CT scan for gastrointestinal or pancreatic NET.

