7.1 AMENDMENT D

We will increase our accrual ceiling for several reasons. The initial sample size calculation was based on a non-inferiority analysis of ⁶⁸Gallium-DOTATATE PET/CT to octreoscan SPECT, the currently used imaging study to detect NETs. Our interim analysis in 50 patients shows that ⁶⁸Gallium-DOTATATE PET/CT is much more accurate than Octreoscan SPECT (overall accuracy of 78% for ⁶⁸Gallium-DOTATATE PET/CT; 60% for Octreoscan SPECT, 74% for triphasic CT scan% in a per patient analysis). Thus, the sample size calculation has been revised to determine if ⁶⁸Gallium-DOTATATE PET/CT is more accurate than CT scan. Based on the data collected, the difference in the diagnostic accuracy between these two imaging techniques is 4% and the proportion of discordant imaging results is 12%. In order to detect 5% difference between these two imaging techniques with 80% power and with 10% discordant rate, 295 patients are required. The comparison is based on McNemar's chi-squared test at the 5% significance level. Thus, we are increasing our accrual ceiling to 295 patients. In addition, in a per lesion analysis between the two imaging techniques (⁶⁸Gallium-DOTATATE PET/CT and triphasic CT), there were discordant results in 30 of the 50 subjects (in 26 patients, ⁶⁸Gallium-DOTATATE PET/CT found additional lesions, in 4 patients CT found additional lesions, 20 patients had concordant (positive or negative) results). Additional reasons to increase the accrual ceiling are: 1) the most accurate way to confirm the results and findings from ⁶⁸Gallium-DOTATATE PET/CT scan is to compare them to pathologic evaluation of resected tumors. Thus far, 21 of 84 subjects have been recommended to have surgical treatment because of metastatic disease detection on ⁶⁸Gallium-DOTATATE PET/CT, and 9 patients have had a surgical procedure with pathology confirming the results (all true positives). Therefore, in order to increase the power of this comparison, an increase in accrual would be necessary. 2) We have used a gamma probe for intra-operative detection of NETs, in two subjects the results were positive and in order to validate this technique, an increase in number of patients would be needed.

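### In unoperated patients PET findings are checked by the same kind of imaging that PET is compared with, no scoring rule is given for PET-only findings, and a few such patients decide the PET-versus-CT test

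*Combined protocol and SAP*

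**What the plan says.** Section 7 names two checks on PET findings. The first is yearly "conventional imaging studies for assessment of changes in lesions which would minimize false positives". The second is that "in patients who require surgery, diagnosis will be confirmed by histopathology". On the size of the operated group, "it is expected that 10-30% of them will require operative intervention", which leaves 70-90% of patients without surgical histology.

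The comparator has changed over the study. Section 7.1 (Amendment D) re-sizes the study at 295 patients for a McNemar comparison of PET/CT accuracy with CT. Section 7.3 drops Octreoscan and makes CT/MRI the comparator. Section 7.2 (Amendment H) raises the accrual ceiling to 390.

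Section 1.2 describes what conventional imaging misses. One cited study found PET superior to CT, MRI and bone scintigraphy for additional sites of disease. Another found metastases beyond CT and/or MRI in 22 of 33 patients.

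Section 7.1 gives interim results in 50 patients at two levels:
- Per patient: accuracy 78% for PET and 74% for CT, a 4% difference with 12% discordance.
- Per lesion: PET found extra lesions in 26 patients, while "in 4 patients CT found additional lesions, 20 patients had concordant (positive or negative) results".

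Section 7.3, in a separate analysis of 131 patients, takes every lesion seen on any of the three modalities as the denominator.

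**The concern.** A reference standard for an accuracy comparison should not depend on either test being compared. Here, for most patients, the named imaging check on PET is of the same type as the comparator. If a lesion was invisible on CT at entry, its continued absence on CT a year later is weak evidence against it. Stability is weak evidence too, since section 1.2 itself refers to slow-growing pancreatic tumours ("Slow-growing PNETs are best treated by complete surgical removal", a remark about treatment).

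What matters is how a PET-positive, CT-negative patient without histology is scored. If the truth is NET, PET is right and CT wrong; if the truth is no NET, the reverse. The same scans therefore fall in opposite cells of the McNemar table depending on an adjudication that the visible text does not define. These are discordant patients, and only discordant patients drive the test.

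The interim figures show that some unstated reference was already in use. With 78% accuracy, PET was scored wrong in 11 of 50 patients. The only pathology that section 7.1 reports is from 9 operated patients, all of them true positives, so that pathology cannot have produced the PET errors.

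**Working it through.** **Inputs (section 7.1).** Difference d = 0.05, discordant proportion pd = 0.10, power 80%, 5% level (two-sided assumed), n = 295. Interim: n = 50, difference 4%, discordance 12%. The ceiling of 390 is from section 7.2.

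**1. Reproduce the plan's figure.** Miettinen's McNemar formula:

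n = [1.96·pd + 0.8416·√(pd² − d²(3 + pd)/4)]² / (pd·d²)

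= [0.196 + 0.8416 × 0.08979]² / 0.00025 = 0.07375 / 0.00025 = 295.0.

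The stated 295 reproduces exactly.

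**2. Turn the assumptions into patients.** With b the proportion where only PET is right and c the proportion where only CT is right, b + c = 0.10 and b − c = 0.05. So b = 0.075 and c = 0.025, or 22.1 and 7.4 patients of 295.

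**3. Effect of one re-scored patient.** The patient leaves b and joins c. Discordance is unchanged and the difference falls by 2/n.

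**4. Power after k re-scored patients.** Normal approximation, with d = 0.05 − 2k/n:

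power = Φ( (d√n − 1.96√0.10) / √(0.10 − d²) )

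| n | k | Difference (points) | z | Power |
|---|---|---|---|---|
| 295 | 0 | 5.0 | (0.859 − 0.620)/0.312 = 0.77 | 78% |
| 295 | 3 | 3.0 | (0.509 − 0.620)/0.315 = −0.35 | 36% |
| 390 | 0 | 5.0 | (0.987 − 0.620)/0.312 = 1.18 | 88% |
| 390 | 3 | 3.5 | (0.684 − 0.620)/0.314 = 0.20 | 58% |

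Full enumeration of the uncorrected McNemar test gives 80.6% at n = 295 and k = 0, so the approximation is slightly low at the start, but the size of the drop is the same. As a fraction of the PET-only-correct cell, re-scoring 10% takes enumerated power from 81% to 49%, and re-scoring one third (about 7 patients) removes the difference.

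**5. Interim data.** Six discordant patients (12% of 50) and a net difference of two (4% of 50) give 4 versus 2. One re-scored patient makes it 3 versus 3.

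**6. Who can be affected.** Only a patient whose NET status rests on the PET finding plus entry evidence that does not establish NET. Section 2.1.1 admits patients on biochemical evidence alone, so a PET-positive, CT-negative patient is possible. Section 7 expects somewhat under 20% of patients to be NET-negative, so the plan does not treat meeting the entry criteria as settling the diagnosis. A patient with established disease elsewhere does not change status because PET shows extra lesions.

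**The case against.** Four objections carry weight.

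- **No rule penalises PET.** A reader might infer that true PET-only findings will be counted as PET errors and CT successes. No passage says that absence or stability on follow-up makes a finding false. The one lesion rule given for unoperated patients, the any-modality denominator in section 7.3, treats every PET-only lesion as real and so favours PET. This stands: the problem is an open reference standard with unknown net direction.
- **The small-tumour figure is not about CT.** A reader might also infer that the protocol says its follow-up imaging misses small tumours, from "identifying >50% of pancreatic NETs larger than 3cm in diameter but only 5% if the tumor was smaller than 1cm". That sentence concerns MRI. Of CT, section 1.2 says: "Computed tomography (CT) has been the most widely used modality with the best sensitivities". CT is the routine study imaging, and MRI is a substitute: "Patients with a severe iv contrast allergy (anaphylaxis with premedication) will have a MRI of the abdomen and pelvis performed". No size-specific CT figure is given, so the MRI figure is no evidence about CT. The support comes from the section 1.2 statements that PET finds sites conventional imaging misses.
- **Few patients are exposed.** The 26 of 50 is a lesion-level count, whereas per-patient discordance was 12%. Every eligible patient has some non-PET evidence at entry. The PET-only-correct cell also includes any PET-negative, CT-positive patients without NET, who cannot be re-scored this way. This limits the number affected, but in step 4 three are enough to matter.
- **Other information exists.** Later CT can confirm a lesion that appears or grows. The précis adds yearly biochemical and clinical evaluation, and the study calendar allows repeat PET in certain patients. None of this is stated as a rule for truth. Section 3.2 (follow-up examinations) was not in the text available for this review and may add detail.

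**Conclusion.** The concern holds as a lack of independence between reference and comparator, joined to a missing scoring rule. In the 70-90% of patients expected to have no surgical histology, the named imaging check on PET is of the same kind as the comparator, and the protocol says that this imaging misses sites PET finds. The documents do not support the stronger reading that the design penalises PET; the bias could go either way.

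No stated figure is wrong. The issue is fragility: three re-scored patients take the difference from 5.0 to 3.0 points and power from about 78% to 36% at 295 patients, or from about 88% to 58% if all 390 enter the test. One patient removes the interim difference. The number three is illustrative, since the documents give no rate of unresolved PET-only patients. The calculation also assumes Amendment D's 5% difference and 10% discordance. Section 7.2 does not say whether all 390 patients enter this test. The lesion comparisons judged against histology in operated patients (sections 7, 7.2 and 7.3) are not affected.

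**What to change.** In section 7:

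- State that absence or stability on follow-up CT/MRI alone neither confirms nor refutes a PET-positive, CT-negative finding.
- Classify such a finding as true or false on histology, on later appearance or growth, or on an established alternative diagnosis. Otherwise call it unresolved.
- Apply the same rule to CT-positive, PET-negative findings, so that the standard is neutral.
- Report the per-patient PET-versus-CT difference three ways: unresolved cases all true, all false, and excluded.

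Because few patients are operated on, PET false positives will be hard to prove under this rule. The all-false analysis guards against that.

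The cost is wording in section 7 and a re-analysis of data already collected, with no new procedures. The downside is that some patients stay unresolved and the reported range is wider.
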